- **Treatment:** Surgical treatment will be performed according to the attending surgeon and is independent of the study. At the conclusion of surgery, they will receive a subcutaneous injection of either Exparel placebo. Patients will receive operative treatment of the hip fracture per the operating surgeon. At the conclusion of surgery, Exparel will be given in 20cc doses, diluted with 40cc of normal saline to make 60cc of total injection volume. The injection solution contains a total of 266mg free base bupivacaine (equivalent of 300 mg bupivacaine HCl). The research pharmacy will prepare the injection solution to contain either Exparel or placebo solution. In intra-capsular arthroplasty cases, the solution will be injected circumferentially into the capsule, surrounding musculature, and subcutaneous layer. In cases with extra-capsular fractures treated with sliding hip screws or cephalomedullary nails, the solution will be administered in the deep tissue and muscles around the fascial incisions as well as in the subcutaneous layer. At the time of medicine or placebo administration, the operating room circulating nurse will create a log entry for Exparel administration in the medication administration record (MAR). This is the section of the medical record where all medications must be recorded, and will be consulted prior to delivery of any other local anesthetic agents, which will serve to limit the additional exposures and minimize the risk of toxicity.
- **Post-operative inpatient care:** While admitted to the hospital, patients will receive medical care per routine, including a standardized post-operative pain control regimen. Post-operatively, all patients will receive a uniform pain control protocol consistent with the current standard of care. We have worked with our anesthesia team to create a consensus-driven protocol to ensure patients are

evaluated for pain and having pain treated in an appropriate and uniform manner. The written protocol is included at the conclusion of this document as Appendix A. We will collect the following data from inpatient hospitalization.

- As a part of the research study regiment, delirium will be assessed using the Confusion Assessment Method (CAM)²⁸, which will be administered 6 hours following surgery, post-operative day 1, 2 and 3 between 8AM-12PM, when a provider is called to the bedside to evaluate the patient for confusion, and also by nursing staff at each nursing shift (Q12).

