The osteoporotic hip fracture population is comprised almost exclusively of geriatric patients, which could be considered a vulnerable population. We will formally use the mini-COG as a screening tool to exclude patients with baseline cognitive impairment. Additionally, patients unable to consent for themselves will be excluded. As such, only cognitively intact patients will be included in the study. Whenever possible, we will also discuss involvement in the study with the patient's family (provided the patient gives permission for us to discuss with them) to ensure that the decision to participate in the study is made with appropriate consideration and that the entire family is comfortable with involvement.

18. Multi-Site Research

This study is being conducted in conjunction with the University of Kentucky, which is a busy academic (level 1) trauma center with a similar hip fracture volume to UMMMC. Funding is divided evenly between both centers, and both have equivalent recruitment goals. The two principal investigators, [name] and [name], are close colleagues who remain in constant communication and will maintain coordination to ensure that:

- All sites have the most current version of the protocol, consent document, and HIPAA authorization.
- All required approvals are obtained at each site (including approval by the site's IRB of record).
- All modifications are communicated to sites and approved (including approval by the site's IRB of record) before the modification is implemented.
- All engaged participating sites safeguard data as required by local information security policies.
- All local site investigators conduct the study appropriately.

- All non-compliance with the study protocol or applicable requirements is reported in accordance with local policy.
- All sites are informed of problems, interim results, and the study closure.

19. Community-Based Participatory Research

Not applicable

20. Sharing of Results with Subjects

To maintain the double-blinded nature of the study, the both researchers and subjects will not be aware of which treatment group a subject has been randomly assigned to. At the conclusion of the study, following de-identification and data analysis, results of this data collection may be shared with patients who have participated in this research as it becomes available, if they request it verbally or in writing. This will only occur after final data analysis, if a subject inquires.

21. Setting

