Research subjects will be identified, recruited and followed post-operatively as inpatients at the University Campus of UMass Memorial Medical Center (UMMMC). They will be followed post-discharge at the Ambulatory Care Center (ACC). Data analysis will primarily occur in locked, private offices at in one of two secure research offices located at the University Campus.

22. Resources Available

UMass Memorial is the largest health system in central Massachusetts. It consists of three separate campuses, Hahnemann, Memorial, and University campus. The Orthopedics Department has locations on all three campuses that each provide a dedicated research space, which contain computers with access to password-protected research drives.

The Principle Investigator (PI) will be responsible for overseeing the study and ensuring consistency throughout the project. The orthopedic PI will serve as the research coordinator and assist in data collection and analysis. Recruitment and consent will be performed by the PI or the research assistant. Each member of the research staff has passed the CITI exam on ethical conduct of research and have received training and supervision regarding patient confidentiality and study protocol. The PI will meet with all research staff periodically to review each role and ensure adequate training for the respective positions. Upon enrollment of each patient, the corresponding surgical team will be counseled concerning the details of the study and their role, prior to admitting the patient into the OR.

The hospital research pharmacy has already been approached about this study and a protocol is in place to ensure appropriate randomization, blinding, and treatment occurs for the study-related portion (injection of Exparel vs. placebo at the conclusion of the operation).

The PI and research assistant will be responsible for institutional /IRB communication as well as data review and assistance with follow-up patient coordination as needed. There are no anticipated adverse consequences associated with this study, however, the principal investigator and research assistant will both be available should any unexpected medical or psychological problems arise. The research subjects will be provided with appropriate contact information in the consent form and will be provided with the PIs contact information at the time of enrollment as well.

23. Prior Approvals

Not applicable

24. Recruitment Methods

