Patients will be given ample time to review the contents of the consent in private. The patient will be approached about the study as soon as they are identified to give them adequate time to review the study information prior to surgery. A researcher will then be available to answer all questions regarding the patient's participation in the study, including but not limited to all risks and benefits. The patient may refuse to participate at any time during the consenting process or over the course of the study.

31. Process to Document Consent in Writing

The consent will be documented in accordance with the guidelines detailed previously in the HRP-803 INVESTIGATOR GUIDANCE: Documentation of Informed Consent. The patient will receive a copy of this consent for their personal records during the enrollment process. This consent has been largely modeled after the Template Consent Document (HRP-502) and provides answers to many anticipated questions. Each signed consent will be stored in a locked cabinet in a secure research office that only approved study personnel are able to access.

32. Drugs or Devices

Exparel (liposomal bupivacaine) is FDA approved, with a labeled indication of "single-dose infiltration into the surgical site to produce postsurgical analgesia". As such, this study represents on-label use of the medication. Use of Exparel post-operatively in this patient population does not involve a novel route or dosage, and is not being used in a patient population that would increase the risks. Exparel is

routinely used during arthroplasty surgery at our healthcare system Memorial Hospital in a population with a similar (although not identical) age profile and medical comorbidity profile. Additionally, this medication was routinely used at other institutions that the PI has trained at in hip fracture patients without identified increased medical risks or complications.

We will maintain coordination with the research pharmacy to store, handle and administer the drug, in accordance with the study procedure. The IDS will be responsible for drug preparation and accountability. Refer to 8. Study Timelines for details on the study procedure. Placebo will consist of normal saline. Exparel is not a clear/transparent solution, so per discussion with the IDS, blinding will be performed by delivery of the medication in an opaque syringe.

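### The opaque syringe masks the barrel but not the injected fluid, so those present at the injection may learn the arm, and nothing described keeps them out of outcome assessment or analysis

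*Protocol*

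**What the plan says.** The title of both documents calls the trial double blinded. Section 20 of the protocol says that "the both researchers and subjects will not be aware of which treatment group a subject has been randomly assigned to".

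Section 32 gives the means. "Placebo will consist of normal saline"; "Exparel is not a clear/transparent solution"; so, after discussion with the pharmacy service, "blinding will be performed by delivery of the medication in an opaque syringe".

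Section 10 describes the injection. "Exparel will be given in 20cc doses, diluted with 40cc of normal saline to make 60cc of total injection volume". In arthroplasty cases, "the solution will be injected circumferentially into the capsule, surrounding musculature, and subcutaneous layer". In screw or nail cases, "the solution will be administered in the deep tissue and muscles around the fascial incisions as well as in the subcutaneous layer".

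Section 22 has the surgical team briefed on the study before each operation. It also says: "The orthopedic PI will serve as the research coordinator and assist in data collection and analysis". The SAP names the tests to be used but says nothing about whether the analyst sees the arm labels.

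**The concern.** The two fluids are acknowledged to look different. The only masking measure described at the point of injection works while the fluid is inside the syringe. Once it is being delivered into exposed tissue, the surgeon, assistants and scrub staff may be able to see what it is.

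This matters because several outcomes depend on someone's judgement. A CAM assessment can be prompted by a provider called for suspected confusion. Complications and readmissions must be identified and coded. Length of stay and discharge disposition are clinical decisions. If a person who has recognised the arm later does any of these tasks, or helps to analyse the data, the comparison is open to bias, while the report would still describe the trial as double blinded.

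**Working it through.** The blinding claim rests on no figure, so the main check sets the sections side by side. A short sensitivity calculation follows.

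**1. What the syringe masks.** The active injection is 20 cc of drug plus 40 cc of saline, 60 cc in all, so the drug suspension is 20/60 = one third of the volume. The documents do not describe how the diluted fluid looks. Under Section 10 the pharmacy prepares the injection solution, and under Section 32 an opaque syringe was still thought necessary. This suggests, without proving, that the prepared dose was expected to look different from saline. Nothing described covers the fluid after it leaves the syringe.

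**2. Whom the claim covers.** Section 20 names researchers and subjects. It does not mention surgeons, theatre staff, ward nurses or outcome assessors.

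**3. Whether those present are kept away from each outcome.**
- *Pain VAS:* recorded by nursing staff every 4 hours (Section 10). No link to theatre is documented.
- *Opioid totals:* Appendix A ties the first two oxycodone steps to pain scores; the breakthrough and rescue steps carry no numeric threshold. The documents do not say whether anyone from theatre orders these doses.
- *CAM:* nursing staff assess every 12 hours. There are also assessments at 6 hours and on the mornings of days 1, 2 and 3, for which no assessor is named, and others when a provider is called for confusion (Section 10).
- *Complications and 30-day readmission:* follow-up after discharge is run by the individual surgeon (Section 10). No one is named to code these outcomes independently.
- *Length of stay and disposition:* the documents do not say who decides.
- *Analysis:* the orthopaedic PI assists (Section 22), and the SAP does not require coded arms.

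The documents describe no look-alike placebo, no injector kept out of later study tasks, no named blinded assessor and no test of whether blinding held.

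**4. Sensitivity of the opioid comparison.** Inputs from the power paragraph of the SAP: 0.52 mg/d, 50 patients, 80% power, significance level 0.05. Assumptions: the plus-or-minus figure is a standard deviation, there are 25 patients per arm, and the test is two-sided.
- Standard error of the difference = 0.52 × √(2/25) = 0.147 mg/d.
- Detectable difference, normal approximation = (1.960 + 0.842) × 0.147 = 0.412 mg/d. With the noncentral t it is 0.4205 mg/d. The plan's 0.42 mg/d is reproduced.
- Suppose there is no true effect and blinding failure adds a bias *b* to the difference. The rejection rate then follows from a noncentral t with 48 degrees of freedom and noncentrality *b*/0.147. For assumed *b* of 0.1, 0.2 and 0.3 mg/d it is 10%, 27% and 52%, against the nominal 5%.

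These values of *b* are arbitrary. On the plan's own standard deviation, a small shift would matter; the calculation does not show that any shift would occur.

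**The case against.** The strongest reply is that much of the route from theatre to outcome is not in the documents, and that safeguards exist. Nurses record VAS and do shift CAMs. Appendix A limits discretion at the first oxycodone steps. The medication record is completed in the same way for drug and placebo, so it does not reveal the arm. Section 22 says that a pharmacy procedure is in place to secure blinding; it is not reproduced and may contain more. All of this stands, and it rules out four stronger readings that a reader might infer:

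- *Blinding fails outright.* Nothing shows that patients or ward nurses learn the arm. Recognition of the fluid in theatre is itself an inference, because the appearance of the diluted product in tissue is not described.
- *The operating team runs ward care, or the PI is at the table.* Neither is stated. Section 10 says only that inpatient care is routine and that surgeons direct follow-up after discharge. Section 22 does not say that the PI operates or injects.
- *The bias must favour Exparel.* Extra opioid given to patients thought to be on placebo would raise their opioid totals but lower their pain scores. The first exaggerates the drug's effect; the second dilutes it.
- *The bias can be sized from one oxycodone dose.* That needs opioid conversion factors from outside the documents and an assumed dose shift in every patient of one arm.

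The reply does not repair the core. The plan concedes a visible difference, names a measure that does not cover the fluid once it is being injected, and describes no separation of roles to make up for it.

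**Conclusion.** The concern holds in limited form. Followed as written, the plan claims double blinding that its stated method does not secure for those present at the injection, and it leaves them free to do study assessments, coding or analysis. The exposure is clearest for provider-prompted CAM, the scheduled CAMs with no named assessor, complication and readmission coding, and analysis. It is weakest for nurse-recorded VAS and shift CAMs.

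The conclusion assumes that the diluted drug remains distinguishable from saline as it is injected. That is probable from Section 32 but not documented, so confidence is medium. Neither the size nor the direction of any bias can be computed from the documents. This is a correction that should be made; it does not show that the results would be invalid.

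**What to change.** In Sections 10, 20 and 32 of the protocol:

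- State that anyone present at the injection is treated as potentially unblinded and does not perform study CAM assessments, code complications or readmissions, or analyse data.
- Assign those tasks to ward nurses and research staff already in the study who were not in theatre. If the PI attends injections, the role given in Section 22 must be narrowed to match.
- Run the final analysis on arms coded A and B before the code is opened, and say so in the SAP.
- Record a treatment guess from the surgeon at the end of surgery, and from the patient and a ward nurse at 72 hours. The surgeon's guess tests the fluid's visibility directly; the 72-hour guesses will partly reflect how well pain was controlled.
- Describe the trial as patient- and assessor-blinded unless masking of the fluid is shown.

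Make no change to opioid ordering or to Appendix A.

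The cost is some role wording and a short questionnaire, with tasks placed among existing staff. The drawbacks are a weaker blinding label and less involvement of the PI in data handling.

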Appendix A: Post-operative Pain Control Protocol

- Preop management
- Intra-op
 - Spinal vs. GETA per anesthesia and orthopaedic surgeon discussion with patient
 - Exparel vs placebo at conclusion of case
- Post-op / floor:
 - Standard PACU / floor pain assessment protocol
 - No toradol
 - Standing Tylenol 650mg PO q6hrs
 - Pain > 4/10, one dose 2.5mg PO oxycodone
 - Pain > 8/10, one dose 5mg PO oxycodone
 - Breakthrough pain: additional oxycodone 5mg PO once
 - Rescue pain: Hydromorphone 0.1mg IV once

Official Title: Does the Use of Liposomal Bupivacaine Decrease Narcotic Requirements in Geriatric Hip Fractures? A Randomized, Double Blinded Control Trial

NCT Number: NCT03289858

Date of Document: August 27, 2017

Statistical Analysis Plan for Randomized Controlled Trial for Exparel Hip Fracture (H00013594)

Primary Outcome Variables: Total morphine equivalents in the post-operative period for 24, 48, and 72 hours, CAM score and average Pain Visual Analog Scale

Secondary Outcome Variables: Length of stay, discharge disposition, timing and participation with inpatient physical therapy, complications and 30 day readmission.

Comparisons between continuous variables will be made using Students t-test, and categorical variables using the Chi-square statistic or Fischer's Exact Test, based on incidence.

Power analysis: Recent studies evaluating regional nerve blocks in hip fractures have shown an average morphine sulfate equivalent of 3.5 +/- 0.52 mg/d in the first 3 postoperative days. That same study showed a 33% reduction in morphine equivalents (3.5 mg/d vs 2.1 mg/d). Assuming a similar effect size, this study would require only 8 patients group to be powered to 80% with a significance level of 0.05. With a target recruitment goal of 50 patients, the study would be powered to detect differences as low as 0.42 mg/d (a 12% effect size)

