H00013594
2018-03-15

Official Title: Does the use of Liposomal Bupivacaine Decrease Narcotic Requirements in Geriatric Hip Fractures? A Randomized, Double Blinded Control Trial

NCT Number: NCT03289858

Date of the Document: March 15, 2018

1. Title

Does the use of Liposomal Bupivacaine Decrease Narcotic Requirements in Geriatric Hip Fractures? A Randomized, Double Blinded Control Trial

2. IRB Review History

N/A

3. Objectives

Decreasing pain and narcotic requirements in the elderly population following hip fracture could be associated with improved outcomes and the prevention of complications. Our goal is to conduct a multi-center prospective randomized control trial to determine if liposomal bupivacaine is superior to standard of care by addressing the below separate but related aims:

1. **Determine the effectiveness of Exparel to reduce narcotic requirements and pain post operatively after hip fracture treatment.** Excess narcotic use in the elderly population is associated with a host of complications often magnified by polypharmacy, including in hospital delirium, increased length of stay, nausea, constipation, urinary retention, respiratory depression and others. Decreasing narcotic usage in this group of patients following hip fracture can possibly reduce such complications. Patients will receive standard of care medical treatment and be randomized to intra-operative Exparel vs. placebo injections. Opioid requirements, complications, pain score, and length of stay will be assessed in the post-operative period.

- **Hypothesis:** We hypothesize that total morphine requirements and pain scores will be decreased in this group following the administration of exparel in the geriatric hip fracture fracture population.

2. **Determine the effectiveness of Exparel to reduce delirium in post-operative hip fracture patients.** In hospital delirium in elderly patients is associated with poor outcomes, including prolonged length of stay, poor participation in rehabilitation, and falls. Use of a locally administered liposomal bupivacaine could decrease the need for additional medications for pain control in addition to decreased mental stress for patients in this unfamiliar situation, thus resulting in decreased episodes of delirium. We will assess delirium utilizing Confusion Assessment Method (CAM) scores in the post-operative period at regularly scheduled intervals and compare average scores between the treatment / standard of care group.

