- **Hypothesis:** We hypothesize that total episodes of delirium will be decreased in the liposomal bupivacaine group.

3. **Determine if Exparel is cost-effective in hip fracture patients.** The costs associated with increased narcotic usage, prolonged stay, resources, and complications can be significant. The use of liposomal bupivacaine may lead to decreased resource utilization to care for hip fractures. We will conduct an economic analysis evaluating total inpatient hospitalization costs including costs associated with length of stay, medication requirements, and resources associated with consultations and diagnostic evaluations. These costs will be compared against the cost of Exparel administration to evaluate the net cost effect of the intervention.

- **Hypothesis:** We hypothesize that the net cost of inpatient care will be decreased when compared to standard of care.

4. Background

Osteoporotic fragility fractures of the hip are common in the geriatric population, are increasing in frequency, and represent a growing social and economic burden^{1,2}. Pain control after surgical treatment is an area of growing interest³, as improvement in post-injury pain is often an important indication for surgical treatment of hip fractures^{4,5}.

Typically a mainstay of post-operative pain control, the use of opiates has come under increasing scrutiny, as it has been shown to be associated with delirium, respiratory depression, and even may even lead to addiction or abuse in the medically frail geriatric population⁶. These concerns have led to efforts to minimize the use of post-operative opiates in hip fracture patients. In that context, a treatment that could reduce the necessity of post-op narcotics while still improving pain control would be potentially valuable.

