- End stage renal disease as defined by patients requiring hemodialysis at least twice weekly
- Polytrauma, defined as:
 - Concurrent upper or lower extremity fracture, pelvis fracture, spine fracture, rib fractures, or facial fractures
 - Blunt chest or abdominal trauma resulting in diagnosed organ injury
 - Head trauma resulting in intracranial bleed or diagnosed concussion
- Allergy to amide-type local anesthetics
- Prisoners (unlikely to be accessible for follow-up)

6. Study-Wide Number of Subjects

This is a multi-center study being conducted in conjunction with the University of Kentucky. The total recruitment goal is 60 patients, with a goal enrollment of 30 patients at University of Massachusetts, and 30 patients at University of Kentucky.

Recent studies evaluating regional nerve blocks in hip fractures have shown an average morphine sulfate equivalent of 3.5 +/- 0.52 mg/d in the first 3 postoperative days²⁶. That same study showed a 33% reduction in morphine equivalents (3.5 mg/d vs 2.1 mg/d). Assuming a similar effect size, this study would require only 8 patients group to be powered to 80% with a significance level of 0.05. With a target recruitment goal of 50 patients, the study would be powered to detect differences as low as 0.42 mg/d (a 12% effect size). Assuming a 10-20% loss to follow-up, we aim to recruit a total of 60 patients studywide (i.e. 30 at each site).

7. Study-Wide Recruitment Methods

Recruitment methods will be the same at both University of Massachusetts and University of Kentucky. Refer to [24. Recruitment Methods](#) for details of recruitment methods at University of Massachusetts.

8. Study Timelines

- Duration of an individual subject's participation in the study

An individual subject's participation in the study begins at enrollment and ends after the 30 day post-op follow-up period.

- Duration anticipated to enroll all subjects

From recent internal data review, we treat between 250-300 hip fractures annually at UMMMC. We anticipate 10-25% of patients will be both eligible and willing to enroll in the study, so to enroll 30 patients should take 6-12 months.

- Estimated date for the investigators to complete this study (complete primary analyses)

Primary analysis should be completed once the final cohort of patients complete their 30 day study window, so we expect 13-14 months after initiation of enrollment.

9. Study Endpoints

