- Adverse events will be monitored and recorded during hospitalization following standard of care regiment and later be used and accessed for data collection of the research study. The adverse events monitored and recorded will include: alteration of mental status, respiratory depression, wound complications, fixation-related complications.
- The following information will be accessed via the electronic medical record after discharge:
 - Total morphine equivalents post-surgery, including and excluding recovery unit administration of narcotics in the immediate post-operative period.
 - Pain Visual Analog Score (VAS) score, which is obtained Q4 by nursing staff.
 - Timing and participation with physical therapy will be recorded looking at time until first therapy evaluation, and level of mobilization achieved
 - Length of stay, discharge disposition
- **Post-hospital follow-up:** Follow up after discharge will be done according to each individual surgeon's practice per their standard of care. It typically involves a follow up appointment at 2-4 weeks post-operatively, with longer follow-up as needed based on the injury type, surgical fixation strategy, and the trajectory of recovery. In addition to data collected as indicated above, including total morphine equivalents post-op period, CAM score, average pain VAS, length of stay, discharge disposition, timing/participation with inpatient physical therapy and adverse complications, data concerning 30-day patient readmission will be collected during the 30-day post-op period.

11. Data and Specimen Banking

No specimens will be obtained or retained for future study. The stored deidentified data from the study will be kept for a minimum of 6 years for records in the event follow-up studies are pursued and will remain protected and encrypted. Data will be permanently deleted following this time period. The banked data will be stored on a password-protected research drive corresponding to "orthotrauma (\\ummcnas03)". Upon conclusion of the study, the data will be stored in a password encrypted file that only the PI has access to.

12. Data Management

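### Five unranked primary outcomes with no success rule: if any one at p<0.05 suffices, the chance of a false-positive primary is roughly 11 to 20%, not 5%

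*SAP*

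**What the plan says.** The SAP lists the primary outcomes in one line: "Total morphine equivalents in the post-operative period for 24, 48, and 72 hours, CAM score and average Pain Visual Analog Scale". Protocol section 9 repeats the list word for word. The only testing rule is in the SAP: "Comparisons between continuous variables will be made using Students t-test, and categorical variables using the Chi-square statistic", with Fisher's exact test as the other option for categorical variables. Neither document has a testing order, a split of alpha, or a requirement that all or some of the primaries succeed.

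The level 0.05 appears only in the power text ("powered to 80% with a significance level of 0.05", SAP and protocol section 6). That text concerns one quantity, average daily morphine equivalents over the first three postoperative days.

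The aims in protocol section 3 do not supply a rule. The Aim 1 hypothesis is that "total morphine requirements and pain scores will be decreased in this group". Aim 2 is a separate delirium question and is described in two ways: its text says the trial will "compare average scores between the treatment / standard of care group", while its hypothesis is that "total episodes of delirium will be decreased in the liposomal bupivacaine group". Protocol section 10 collects "Total morphine equivalents post-surgery, including and excluding recovery unit administration of narcotics" and does not say which version is the primary.

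**The concern.** With five primaries and no rule, a report could call the trial positive on whichever one reaches p<0.05, and the plan as written would not contradict it. The 0.05 used for sizing is then not the trial's error rate.

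Two open definitions widen the choice. The opioid total can include or exclude recovery-unit doses. Delirium can be an average score (t-test) or a count of patients or episodes. Either choice could be made after the data are seen.

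A stricter reading of Aim 1, in which opioid use and pain must both fall, does not inflate the error. It has no stated power, however, and still does not say which of the three opioid time points must succeed.

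**Working it through.** **The plan's own figure.** Inputs from the SAP and protocol section 6: SD 0.52 mg/d, 50 patients, 80% power, alpha 0.05. Equal allocation (25 per arm) is assumed.

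- Normal approximation, two-sided: 0.52 × √(2/25) × (1.960 + 0.842) = 0.412 mg/d. The exact t-test gives 0.421.
- The stated 0.42 mg/d therefore reproduces, and 0.42/3.5 = 12%. One-sided 0.05 would give 0.52 × √(2/25) × (1.645 + 0.842) = 0.366, so the plan used a two-sided test.

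**Ceiling.** Five independent tests at 0.05: 1 − 0.95^5 = 0.226. The opioid totals are nested, so this cannot be reached. If daily doses have equal variance and common correlation ρ, the totals to day j and day k (j<k) correlate at √[ j(1+(k−1)ρ) / ( k(1+(j−1)ρ) ) ]. Even at ρ = 0 this gives 0.71 (24 and 48 h), 0.82 (48 and 72 h) and 0.58 (24 and 72 h).

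**Simulation with no treatment effect.** The documents give no correlations and no delirium rate, so these are assumptions: 25 per arm, multivariate normal outcomes, opioid totals as running sums of three days, daily-dose correlation 0 to 0.8, correlation across outcomes 0 to 0.5, delirium rate 10% or 25%. There were 22 scenarios of 20,000 trials each.

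| Result at p<0.05 | Chance |
|---|---|
| Any of five, CAM by t-test | 14.1 to 19.8% |
| Any of five, CAM by Fisher's test | 11.4 to 17.3% |
| Any of five, CAM by chi-square | 14.6 to 20.1% |
| Any of five, favouring treatment (t-test or Fisher) | 5.6 to 10.4% |
| Any of the three opioid totals alone | 6.9 to 10.9% |

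Fisher's test gives lower figures because its actual size here is only 0.8 to 2.3%.

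**Second calculation.** Five correlated z-statistics, 400,000 draws per scenario, each tested two-sided at 0.05:

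- Uncorrelated daily doses, with VAS and CAM independent of everything else: 19.4%.
- Daily correlation 0.5, opioid–VAS 0.5, CAM correlations 0.3: 16.1%.
- Daily correlation 0.9, opioid–VAS 0.7, CAM correlations 0.6: 12.4%.
- Every pair at 0.9: 10.1%.

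**Aim 1 alone.** For the four Aim 1 tests (three opioid totals and VAS), with daily correlation 0 to 0.8 and VAS correlated 0 to 0.9 with the 72 h total, the chance of at least one p<0.05 is 11 to 16%.

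**Cost of splitting alpha.** Five primaries at 0.01 keep the error at or below 5 × 0.01 = 0.05. The detectable difference at 25 per arm becomes 0.52 × √(2/25) × (2.576 + 0.842) = 0.503 mg/d (normal) or 0.521 (t-test), and 0.521/3.5 = 14.9%. Power for 0.42 mg/d falls from 79.9% to 57.2%.

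**The case against.** The strongest reply is that no text says any one primary suffices. The title, Aim 1 and the only power calculation all point to opioid use as the lead outcome. The list can be read as three outcomes, one of them reported at three times. Delirium has its own aim, and whether separate aims must share one 5% is partly a matter of judgement. On that reading the inflation is 7 to 11%. This is fair, and it is why the figures are conditional. It does not supply a rule: emphasis on opioids does not choose among three time points, and Aim 1 taken alone still gives 11 to 16%.

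The correlations may also be higher than assumed, because Appendix A ties oxycodone to the pain score. With daily correlation 0.9, cross-outcome correlation 0.7 to 0.8 and Fisher's test for CAM, the range is 9.5 to 10.9%. That moves the lower end to about 10%, a small shift. Fisher's test would also be the usual choice at a 10% delirium rate (expected count 25 × 0.10 = 2.5 per arm), so the chi-square figures matter mainly at the higher rate.

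Protocol section 10 places recovery-unit doses in the immediate post-operative period, which suggests that inclusion is the default. That is reasonable, but the section lists both versions and names neither as primary.

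The power text has faults of its own: 3.5 to 2.1 mg/d is 1.4/3.5 = 40%, not 33%, and its figure of 8 patients does not reproduce as a per-group number (3 to 4 suffice). There is also no rule for patients discharged before 72 h. These are separate points that the proposed change neither creates nor cures.

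**Conclusion.** The concern holds. The core defect is the missing decision rule: five primaries, no ranking, no adjustment and no success criterion. If any one at p<0.05 suffices, the chance of at least one false-positive primary is roughly 11 to 20%, or about 10% under stronger correlations. The 22.6% for independence is a ceiling only.

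All these figures assume 25 per arm and rest on correlations and delirium rates that the documents do not give. That no adjustment is intended is inferred from the documents' silence. If all five had to succeed, the error would be at most 5%, but no joint power is stated. The choice between recovery-unit versions would add to the range by an amount that cannot be computed from the documents. The point must be fixed because it governs the trial's main claim.

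**What to change.** Name the 72 h total morphine equivalents as the single primary, tested at two-sided 0.05. That total is three times the three-day daily mean in the power text, so difference and SD scale together and the change by itself needs no new sample size. Before unblinding:

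- State whether the total includes recovery-unit doses, and make the other version a sensitivity analysis.
- Move the 24 h and 48 h totals, VAS and delirium to key secondaries, tested in an order fixed by the sponsor or with a Holm adjustment. If the overall 5% is to cover them as well, test them only after the primary succeeds.
- State whether delirium means the average CAM score or delirium episodes, because this decides the test.

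Alternatively, keep five primaries at 0.01 each and restate the detectable difference as about 0.52 mg/d (14.9% of 3.5). That figure covers only the three-day opioid mean; the documents give no SDs from which to restate the others.

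The cost is wording in the SAP and protocol section 9, with no extra patients. A nominally significant 24 h, VAS or CAM result could no longer carry a primary claim alone. Delirium, the whole of Aim 2, loses primary status and might not be formally tested if placed late in a fixed order; Holm removes the dependence on position at some loss of power. With the 0.01 alternative, power for 0.42 mg/d falls from 80% to 57%. If the sponsor prefers another single primary, the same structure applies, but that outcome needs its own power statement.
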